8.2 PROPOSED ANALYSES

Descriptive statistics will be prepared to show the mean, standard deviation and range for the outcome variables in the fixed and removable Twinblock groups.

The primary outcome measure will be millimetre change in overjet per month. This will be compared between the fixed Twinblock group and the removable Twinblock control group using a Multilevel Linear Model (MLM). This will allow us to assess the difference between treatment groups while controlling for any differences in effect between treatment centres. In the event that the collected data violates the assumptions for a parametric test, heterogeneity between centres will be assessed using the MLM and checked with a Friedman's ANOVA within treatment groups. If no heterogeneity between returning centres is observed, data from all centres will be collapsed and a bootstrapped independent t-test will be run. If both non-parametric data and heterogeneity between centres and a Bonferroni correction will be applied for running multiple analyses. Estimates of effect size will be calculated from the data to better inform the sample size calculations of future studies.

The effect of the Twinblock appliance upon secondary measures will be explored using descriptive statistics. Data on the patients' perceptions and experience of their appliances will be analysed with descriptive statistics to produce graphs and tables

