However, like all removable functional appliances, compliance with the removable Twinblock appliance can be problematic. The issue with compliance has been quantified by Parekh et al (2019) for the Twinblock appliance at mean daily wear of 12.38 hours or 51.6% of that recommended. Furthermore, age is also a factor in compliance with O'Brien et al. (2003c) finding older patients had unusually high failure rates (34%) compared to younger patients (O'Brien et al. 2003a) at 19%. The solution to the problem of compliance is to use a fixed functional appliance. The oldest known fixed functional appliance is the Herbst appliance which was first described at the start of the 20th century and re-introduced by Hans Pancherz more recently. It is comprised of two maxillary and mandibular sections – either cast or banded. However, problems include breakages, regular re-cementing of the appliance, and patient acceptance. The most recent version of the Herbst appliance was used in the UK MRC-funded multicentre RCT (O'Brien et al. 2003c) comparing the removable Twinblock appliance with the Herbst. The rate of failure during the functional phase was surprisingly high in the Twinblock group at 34%, and much lower in the Herbst group at 13%.

Combining the extensive research literature on the Herbst appliance with clinical experience produces the following summary:

- The Herbst appliance reduces almost all overjets in 6 months which compares to an average of nine months with the removable Twinblock appliance
- Patients find the Herbst appliance not excessively intrusive after the first week like the removable Twinblock appliance
- There is an inconveniently high rate of decementation, mechanical failure and lower incisor proclination with the Herbst appliance
- A functional appliance that can be rapidly and reliably added to a conventional fixed appliance will probably prove very popular.

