5.5 RANDOMISATION

5.5.1 Randomisation

Randomisation will be stratified by gender, overjet measurement (IOTN 4a or 5a) and site, using the on-line TCTU (TRuST – Tayside Randomisation System) randomisation system. TCTU's Randomisation System (TRuST) provides GCP compliant web-based randomisation to produce balanced randomisation allocation based on a minimisation with stratification algorithm.

The system has been built to deal with each combination of variables by making up a block, which is how the participants are stratified across at point of randomisation. However, to make it more difficult to predict the allocation it uses random block sizes. Therefore, over time it will keep the variable balanced, with an automatic notification from the system to stop recruiting to a particular group.

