6 DATA COLLECTION& MANAGEMENT

6.1 DATA COLLECTION

Overjet measurement

Overjet will be measured (in millimetres) between the upper incisal edge and the labial surface of the lower incisors using a metal ruler at all appointments to assess rate of reduction. This will be measured at start of treatment (T0), 3 months (T1), 6 months (T2), 9 months (T3), end of Twinblock appliance phase, i.e., when overjet has reduced to 0-3mm and remains unchanged at two consecutive appointments (T4), for a maximum of 12 months from start of treatment and end of fixed appliance treatment (T5). If overjet has reduced earlier than anticipated, follow-up time points will be skipped to T4 and T5.

Impressions

A negative imprint of teeth and soft tissues will be made using alginate impression material to produce plaster models (positive reproduction), allowing fabrication of the fixed and removable Twinblocks at the Orthodontics laboratory within Dundee Dental Hospital. A typical impression takes 10 minutes and is routine procedure for all patients undergoing Orthodontic treatment.

Intra oral scans

3Shape Trios® or iTero Element ® will be used to record intra- Oral scans for digital study models. These use a non-contact laser scanning technology to record a three-dimensional record of the tooth position and occlusion. A scan takes 10 minutes to collect depending on operator experience and patient compliance. There is no discomfort or sensation associated with the scanning procedure. The pre- and post-treatment study models are essential records in orthodontics and the digital version will allow precise tracking and quantifying (mapping) of tooth movements during treatment. The mapping of teeth movements will provide details of the extent of dental contributions in overjet reduction. If an intraoral scanner is not available at a site, the impression or plaster models will be scanned using the 3Shape dental lab 3D scanner. The superimposition function on 3Shape Ortho Analyzer software will be used to calculate distance between pre- and post-treatment scan landmarks in millimetres.

Stereophotogrammetry

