8 STATISTICS AND DATA ANALYSIS

8.1 SAMPLE SIZE CALCULATION

The feasibility study conducted by us in Dundee Dental Hospital (REC 17/ES/0126) has produced a clear route of progression (NIHR criteria) to the substantive multicentre RCT by estimating all the important parameters. Using initial data obtained from our feasibility study, for an effect size of 0.80 (difference of 81 days and SD 101 days), an alpha value of .05 and a power of 80% the required sample size was computed as 26 participants per group giving a total of 52. This is a assuming a simple independent t-test analysis and utilising sample size software PASS20. Recruitment will be across 4 sites and so randomisation will be stratified by site. With the long nature of treatment and high levels of drop out, combined with missing data from non-treatment visits we decided to allow for 40% drop out or incomplete data collection and therefore 88 patients will be recruited, 44 to each arm of the trial.

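### The primary analysis names only centre as controlled for, although allocation is also balanced on sex and overjet class and baseline overjet is measured: an avoidable, probably modest loss of precision

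*Protocol*

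**What the plan says.** All references are to the protocol; no SAP was available.

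- **Allocation (5.5.1).** "Randomisation will be stratified by gender, overjet measurement (IOTN 4a or 5a) and site". The system is described as giving "balanced randomisation allocation based on a minimisation with stratification algorithm". Section 8.1 mentions only one of the three factors: "Recruitment will be across 4 sites and so randomisation will be stratified by site".
- **Outcome (8.2).** "The primary outcome measure will be millimetre change in overjet per month".
- **Primary model (8.2).** A multilevel linear model, with the stated purpose: "This will allow us to assess the difference between treatment groups while controlling for any differences in effect between treatment centres". Sex, overjet class and baseline overjet are not mentioned anywhere in section 8.
- **Fallback (8.2).** If parametric assumptions fail and centres do not differ, "data from all centres will be collapsed and a bootstrapped independent t-test will be run". This drops centre as well.
- **Baseline and end of phase (4.11, 6.1).** Entry requires an overjet of at least 6 mm, with no upper limit. Overjet is measured at T0. The Twinblock phase ends "when overjet has reduced to 0-3mm and remains unchanged at two consecutive appointments (T4), for a maximum of 12 months" from the start of treatment.

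**The concern.** When allocation is balanced on a factor that predicts the outcome, the treatment estimate varies less from trial to trial than a model without that factor assumes. The reported standard error is then too large, the interval too wide and the test conservative. Here two of the three balancing factors are missing from the stated analysis.

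Baseline overjet is the natural candidate for a predictor. Treatment ends at a residual of 0-3 mm, so a patient who starts with a larger overjet and reaches T4 must have had more mm corrected. The protocol treats overjet as important enough to balance on, but not to analyse with. At stake is precision in a small trial (52 planned completers), not the validity of the comparison.

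**Working it through.** **1. The plan's own figure.** Inputs from 8.1: difference 81 days, SD 101 days, alpha 0.05, power 80%, independent t-test.
- d = 81/101 = 0.802, taken as 0.80.
- The two-sided non-central t calculation gives n = 25.5, so 26 per arm. Power at 26 per arm is 80.7%.
- Dropout: 26/(1 - 0.40) = 43.3, so 44 per arm and 88 in total.

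The plan's figures reproduce. They contain no covariate adjustment.

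**2. How strongly could baseline overjet predict the outcome?** The protocol does not say, so this is an illustration. Assume T4 overjet uniform on 0-3 mm and baseline uniform from 6 mm to an upper value of 10 to 14 mm.
- Correlation with *total* mm corrected is sqrt[var(baseline) / (var(baseline) + var(T4))]. The T4 variance is 9/12 = 0.75. With baseline on 6-10 mm the variance is 16/12 = 1.33, giving 0.80. On 6-14 mm it is 64/12 = 5.33, giving 0.94.
- Correlation with mm *per month* was simulated with treatment time centred on 274 days (the nine months quoted in section 2), SD 101 days, limited to 60-365 days. It is 0.28 to 0.41 if time does not depend on baseline, and about 0 if time rises in proportion to baseline.

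I therefore take r from 0 to 0.5.

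**3. Gain from adjustment.** The residual SD is multiplied by sqrt(1 - r²). The unadjusted interval is wider by 1/sqrt(1 - r²) - 1, and the effective d is 0.80/sqrt(1 - r²).

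| Assumed r | sqrt(1 - r²) | Unadjusted interval wider by | Power, 26 per arm | n per arm for 80% |
|---|---|---|---|---|
| 0 | 1.000 | 0% | 80.7% | 26 |
| 0.2 | 0.980 | 2% | 82.3% | 25 |
| 0.3 | 0.954 | 5% | 84.3% | 24 |
| 0.4 | 0.917 | 9% | 87.0% | 22 |
| 0.5 | 0.866 | 15% | 90.4% | 20 |

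At the illustrated r of 0.28 to 0.41 the excess width is about 4-10%. These are ceilings: the formula ignores the degrees of freedom spent on covariates and chance imbalance.

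**4. Check by simulation.** 52 patients, four sites, random permuted blocks within overjet class (a median split of baseline) by sex, 4,000 runs per setting, outcome SD 1, effect 0.8.

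| r | Model SE, centre only | True SE, centre only | Type I error, centre only | Power, centre only | Power with class, sex and baseline |
|---|---|---|---|---|---|
| 0 | 0.285 | 0.286 | 5.0% | 78% | 77% |
| 0.3 | 0.285 | 0.280 | 4.7% | 79% | 81% |
| 0.5 | 0.285 | 0.269 | 3.9% | 79% | 87% |

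Adding class and sex alone brought type I error back to about 5% (5.2% at r = 0.3, 5.6% at r = 0.5). A separate simulation balancing only the two-level class gave about 4.5% at r = 0.3 and 3.1% at r = 0.5-0.55. The unadjusted type I error is thus about 5% at r = 0 and 3-4% at r = 0.5.

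**The case against.** **The protocol does not say that only centre is adjusted for, and an SAP may list covariates.** This is fair as far as the multilevel model goes. But 8.2 does more than leave a gap: it names the model, its purpose and a fallback, and what it names does not match 5.5.1. A pooled two-sample test has no place for any balancing factor.

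**The outcome is a rate, not total mm.** This stands. A reader might infer that baseline overjet largely determines the outcome. That holds for total mm corrected, but a larger overjet may also take longer, and the correlation with mm/month could be near zero.

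**The test remains valid.** This also stands. Randomisation prevents bias, a conservative test is still valid, and the sample size was set without adjustment.

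Three stronger readings are tempting and not supported:
- *Loss of power through four centres.* The wording about differences in effect could be taken as a random treatment slope tested on about 3 degrees of freedom. With non-centrality 0.8 × sqrt(13) = 2.88, power would be 50.4%. Section 8.2 specifies neither a random slope nor a degrees-of-freedom method. Under a centre intercept there are 52 - 1 - 1 - 3 = 47 degrees of freedom and power is 80.7%.
- *A severely conservative test.* If all the variance explained by baseline overjet were balanced, type I error would fall to 1.9% at R² = 0.3. But 5.5.1 balances only the two-level class, so the effect is smaller.
- *Age as a required covariate.* Section 2 reports that "older patients had unusually high failure rates (34%) compared to younger patients", but this compares failure rates between separate cited trials, not mm/month, and age is not a balancing factor.

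**Conclusion.** The point holds as a mismatch between how patients are allocated and how the primary outcome is to be analysed. It is an improvement available at no cost, not a flaw that invalidates the plan. Its size depends on a correlation that the protocol does not give. It is nil at r = 0, about 4-10% in interval width at the illustrated r of 0.28 to 0.41, and 15% at r = 0.5. The corresponding power at 26 per arm runs from 81% to at most 90%. The figures assume 52 completers, an effect of 0.8 SD, a linear relation with baseline overjet and one rate per patient. Nothing here shows bias or an underpowered trial: the stated 80% power never relied on adjustment.

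**What to change.** In section 8.2:
1. State that the primary model for mm/month contains treatment, baseline overjet at T0 as a continuous variable in mm, sex, and site (four sites, as a centre main effect or intercept).
2. Carry the same covariates into any fallback, for example by bootstrapping the adjusted treatment difference in place of the two-sample test.
3. Report treatment differences by site descriptively, and reword the sentence on differences in effect so that it cannot be read as a random treatment slope in the primary test.

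If an SAP exists, it should carry the same model. The cost is wording, provided that the change is made before analysis. Sex, overjet class and site are held at randomisation and overjet is measured at T0. Baseline overjet and sex together use two degrees of freedom. If neither predicts the outcome, the loss is trivial (simulated power 77% against 78%).

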4 TRIAL DESIGN

4.1 INTERVENTION

Participants will be treated either the fixed or removable Twinblock appliances. Following completion of the Twinblock treatment, all participants will continue treatment with fixed orthodontic appliance (train-track braces), which isstandard treatment protocol following completion of twinblock treatment.

[figure not shown]
4.2TRIAL DESCRIPTION

We plan to undertake a multicentre randomised clinical trial in Tayside and Grampian regions as a two-arm parallel design to detect a difference between the fixed and removable Twinblock appliance for overjet reduction.

			Time p	points		
Data collection	T0 Start	T1 3 months	T2 6 months	T3 9 months	T4 End of Twinblock treatment	T5 End of treatment
Clinical Orthodontic assessment	~				✓	~
Overjet measurement	~	~	\checkmark	~	✓	~
Lateral cephalogram	~				✓	✓ (near end)
Impressions / intraoral scan	~				✓	~
3D Facial Stereo – photogrammetry Image	~				✓	~
Patient Experience Questionnaire	\checkmark	~			~	

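### The fallback for the primary analysis checks centres with a test that needs matched data, pools on a weak pre-test, and ends in an incomplete Bonferroni branch

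*Protocol*

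**What the plan says.** Section 8.2 of the protocol fixes the endpoint: "The primary outcome measure will be millimetre change in overjet per month". The main analysis is an MLM comparing the two arms while controlling for centre. A fallback follows, opened by "In the event that the collected data violates the assumptions for a parametric test". It has three steps.

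- **Check of centres:** "heterogeneity between centres will be assessed using the MLM and checked with a Friedman's ANOVA within treatment groups".
- **No heterogeneity seen:** "If no heterogeneity between returning centres is observed, data from all centres will be collapsed and a bootstrapped independent t-test will be run".
- **Heterogeneity seen:** "If both non-parametric data and heterogeneity between centres and a Bonferroni correction will be applied for running multiple analyses". As it stands, this sentence has no main clause. It names no test, no number of analyses and no way of reaching one conclusion.

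Section 4.2 describes the trial "as a two-arm parallel design to detect a difference between the fixed and removable Twinblock appliance for overjet reduction". Section 8.1 gives four sites. Section 5.5.1 stratifies randomisation by gender, overjet category and site.

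**The concern.** Each step of the fallback has its own fault.

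- **The test does not fit the data.** Friedman's test ranks values within a block, where the same subject or matched set is seen under every condition. Within one arm of a parallel trial, each site holds different children, so there are no blocks. A within-arm comparison also asks whether centres differ in level. The question that bears on the treatment comparison is whether the treatment effect differs between centres.
- **The gate treats absence of evidence as evidence.** With few patients per centre and arm, real differences between centres will often go unseen. The analysis then drops the site factor on which randomisation was stratified.
- **The last branch gives no single answer.** It promises several corrected analyses where the primary objective asks one question.

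At stake is whether the primary comparison would have one defined, adequately powered answer if the rates turn out skewed.

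**Working it through.** **Inputs.** Section 8.1: difference 81 days, SD 101 days, alpha 0.05 (taken as two-sided), power 80%, 26 completers per arm, 40% loss, 44 recruited per arm, 4 sites. The split across sites is not stated. I assume it is equal: 26/4 = 6.5 completers, or 44/4 = 11 with no loss, per arm per centre. The effect size of 0.80 comes from a time in days and is used here only as a standardised difference.

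**Step 1: the plan's own figure.** d = 81/101 = 0.802. Normal approximation: n = 2(1.960 + 0.842)²/0.802² = 24.4, so 25 per arm. The exact t calculation gives 25.4, so 26. Inflation: 26/0.6 = 43.3, so 44 per arm and 88 in all. The sample size reproduces. One comparison of 26 per arm has about 81% power.

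**Step 2: can Friedman's test be used?** With b blocks and k centres, the statistic is 12/[bk(k+1)] × ΣRj² − 3b(k+1), where Rj sums the within-block ranks of centre j.

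- Unequal centres: 26 completers over 4 sites cannot split equally (for example 7, 7, 6, 6). There is then no b, and the software returns an error.
- Equal centres: the blocks must be invented by lining up unrelated patients. On one simulated set of 4 centres × 6 patients, 5,000 re-orderings within centre moved the p-value between 0.04 and 1.00 (central 95%: 0.20 to 0.94). Kruskal-Wallis, which needs no blocks, gave one value, 0.58.
- Treating visits as blocks does not help, because that would test change over time.

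**Step 3: how informative is the gate?** Replace Friedman's test with a valid one, Kruskal-Wallis within one arm at 0.05, by simulation. The centre differences are assumptions.

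| Assumed centre differences | Patients per centre | Power |
|---|---|---|
| Shifts -0.5, 0, 0, +0.5 SD | 6 | about 19% |
| Shifts -0.5, 0, 0, +0.5 SD | 11 | about 40% |
| Between-centre SD 0.3 | 7, 7, 6, 6 | about 14% |
| Between-centre SD 0.5 | 7, 7, 6, 6 | about 29% |
| Between-centre SD 0.8 | 7, 7, 6, 6 | about 57% |

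Not observing heterogeneity is therefore weak support for pooling.

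**Step 4: what does pooling cost?** Under the shifts -0.5, 0, 0, +0.5 SD with 6 per cell, the pooled t-test has a type I error of about 3.3% to 3.9%, below the nominal 5%. In one run its power was 72%, against 75% for the centre-adjusted comparison. It is mildly conservative and not biased.

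**Step 5: the last branch.** Suppose it means one t-test per centre at 0.05/4 = 0.0125. With m per arm per centre, the noncentrality is d√(m/2) on 2m − 2 degrees of freedom.

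- m = 6: 0.80 × √3 = 1.39, power about 9%.
- m = 7: 0.80 × √3.5 = 1.50, power about 12%.
- m = 11: 0.80 × √5.5 = 1.88, power about 22%.

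With d = 81/101, the chance that at least one of four tests is significant is 1 − (1 − 0.106)⁴ = 36% at 6.5 per arm, or 1 − (1 − 0.223)⁴ = 64% at 11. Neither is a test of the overall treatment effect.

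**The case against.** The strongest reply is that this is a contingency behind a sound main analysis. That stands: nothing here faults the MLM, and if its assumptions hold, none of this text is used. Four further points limit the concern.

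- **Friedman's test is the secondary check.** The MLM makes the assessment. It would be wrong to say that Friedman's test alone decides pooling.
- **Row order seldom moves the gate.** A reader might infer from the range 0.04 to 1.00 that the primary conclusion turns on how rows are sorted. The documents and figures do not support that. In 30 simulated data sets with Kruskal-Wallis p of 0.40 to 0.55, re-ordering took Friedman's p below 0.05 in about 0.1% of orders. It mattered mainly when the Kruskal-Wallis p was below about 0.2. The test remains undefined for these data, but its practical effect is usually small.
- **The harms partly offset each other.** If the gate usually passes, the last branch is rarely reached, and the usual result is the pooled bootstrapped t-test, which is only slightly conservative.
- **The last sentence may have lost words.** Whether the clause is absent from the source or fell out when the text was read cannot be settled here. Testing centre by centre is a natural reading, but the protocol does not say so.

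A criterion for violated assumptions and a threshold for heterogeneity may properly sit in a statistical analysis plan, so their absence is not counted. What the protocol itself fixes is an inapplicable test, a pooling gate, and a Bonferroni correction over several analyses.

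**Conclusion.** The point holds for the fallback only. The Friedman check is wrong as written. The pooling gate is weak: a valid test would find the assumed ±0.5 SD shifts in about 19% to 40% of cases. The heterogeneous branch is incomplete. Read as one test per centre, it would have 9-22% power per test and no single primary answer. These figures assume equal recruitment at four sites, d = 0.80, a two-sided alpha and the stated centre shifts. The protocol gives neither the split nor the centre differences.

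A reader might go further and call any fallback result arbitrary or uninterpretable. That is not supported, because the branch most likely to be used gives a valid, mildly conservative comparison. Should-fix.

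**What to change.** Delete the Friedman check, the pooling gate and the Bonferroni branch from section 8.2. Keep one centre-adjusted treatment estimate whatever the residuals look like: the planned MLM, or the same model with centre as a fixed effect.

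If residuals are clearly non-normal, keep that same estimate and base its p-value on a permutation test that re-allocates treatment within centre. Take the confidence interval by inverting that test or from a studentised bootstrap. Do not use a percentile bootstrap within centre-by-arm cells: with 6 per cell its 95% interval gave a type I error of about 7% to 8% in simulation. Report treatment-by-centre results descriptively, and let them decide nothing.

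The cost is a wording amendment before outcome data are analysed, plus slightly more analysis work. No patients, visits or data are added.

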3.1.2 Secondary Objectives

- 2. Does the fixed Twinblock appliance produce more skeletal than dentoalveolar contribution for a Class II division 1 malocclusion in comparison to the conventional removable Clark Twinblock appliance?
- 3. Does the fixed Twinblock appliance produce more facial volume increase in comparison to the conventional removable Clark Twinblock appliance?
- 4. Are patient's treatment experience better with the fixed Twinblock appliance as compared to the removable Twinblock appliance.
- 5. Is the fixed Twinblock appliance more cost effective and safer for correcting increased overjets as compared to the removable Twinblock appliances.

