3.2.2 Secondary Outcomes

- 2. Relative skeletal, facial and dentoalveolar contributions to overjet correction by comparing lateral cephalogram changes via cephalometric analyses (Mills 1982), and facial volumetric changes (Camison et al 2018) and tooth movements by superimposing 3D scans, respectively, at the end of orthodontic treatment.
- 3. Patients' perception and experience with the fixed and removable Twinblock appliance will be assessed using the three questionnaires approach (Pre-Treatment questionnaire, Orthodontic Experience Questionnaire and Post-Treatment questionnaire (Al-Naseri et al 2017)
- 4. Cost-effectiveness of overjet reduction with fixed and removable Twinblock by comparing direct costs of treatment i.e., number of visits for Twinblock phase of treatment and number of breakages/loss with the fixed and removable Twinblock appliances.
- 5. Potential adverse effects of the fixed Twinblock and removable Clark Twinblock appliance.

Table 1: Primary Objectives and Outcome Measures

Primary Objective:	Outcome Measure:	Timepoint of outcome measured
Rate of Overjet correction	change in millimetre/month from clinical measurements	T0, T1, T2, T3, T4, T5

Table 2: Secondary Objectives and Outcome Measures

Secondary Objective:	Outcome Measure:	Timepoint of outcome measured
Skeletal, facial and dentoalveolar contributions to overjet correction	Lateral cephalometric analyses, Facial volumetric changes, and tooth movements by superimposing 3D scans	T0, T4, T5
Patients' perception and experience	Pre-Treatment questionnaire, Orthodontic Experience Questionnaire and Post- Treatment questionnaire	T0, T1, T4
Cost-effectiveness of treatment	Number of visits for Twinblock phase of treatment and number of breakages/loss	Τ4

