Vectra® H1 handheld 3D camera will be used to record the patient's three-dimensional (3D) facial characteristics, allowing quantification of 3D soft tissue volume changes. The camera works like any other and would require three facial captures which are automatically stitched into one 3D image with the provided software. The whole process will take 10 minutes. The need for 3D quantification of the soft-tissue effects of functional appliances has been highlighted (Flores-Mir 2006). The immediate soft tissue effects, especially of the soft tissue chin (Sharma 2005) have been shown to be only 40% of the predicted outcome (Salloum 2018). Landmarking of the pre- and post-treatment 3D images will be done using the VAM (Vectra Analysis Module) software and superimposed to measure the difference in linear distance in millimetres.

Lateral Cephalogram

Cephalometric radiographs are routinely taken as part of assessment and planning for orthodontic treatment. Modern digital lateral cephalometric radiographs are very low dose. It is used to assess whether the aetiology of malocclusion is due to skeletal relationship, dental relationship or both and quantify treatment changes. The radiographs will be taken at baseline, end of twinblock treatment and towards end (near end) of fixed appliance treatment in accordance with normal clinical practice. Eastman cephalometric analysis (Mills, 1982) will be done on the radiographs to assess the skeletal and dental changes associated with both the groups. The analysis will include angles SNA (sells-nasion-point A), SNB (sella-nasion-point B), ANB (difference between SNA and SNB), upper incisor long axis to maxillary plane (anterior nasal spine -posterior nasal spine), lower incisor to mandibular plane (gonion-menton), MMPA (maxillary-mandibular plane) and linear measurements - facial proportion (ratio of lower face height to total anterior face height) and APog (tip of lower incisor form line connecting point A-Pogonion)

Patient Experience questionnaire

This validated questionnaire, based on the three-questionnaire approach, will evaluate patients perception of their malocclusion pretreatment (T0) and patients' experience with wearing the fixed and removable Twinblock appliances 3 months into treatment (T1) and at the end of Twinblock phase of treatment (T4).

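### Secondary objectives 2–5 ask fixed-versus-removable questions, but section 8.2 gives them descriptive statistics only; the facial-volume objective also has no volume measurement step

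*Protocol*

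**What the plan says.** Section 3.1.2 sets four secondary objectives, numbered 2 to 5, and each compares the two appliances.

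- Objective 2: "Does the fixed Twinblock appliance produce more skeletal than dentoalveolar contribution for a Class II division 1 malocclusion in comparison to" the removable appliance.
- Objective 3: "Does the fixed Twinblock appliance produce more facial volume increase in comparison to the conventional removable Clark Twinblock appliance".
- Objective 4 asks whether patients' experience of treatment is better with the fixed appliance.
- Objective 5: "Is the fixed Twinblock appliance more cost effective and safer for correcting increased overjets as compared to the removable Twinblock appliances".

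Section 8.2 assigns the analysis. By arm: "Descriptive statistics will be prepared to show the mean, standard deviation and range for the outcome variables in the fixed and removable Twinblock groups". For the secondary outcomes: "The effect of the Twinblock appliance upon secondary measures will be explored using descriptive statistics". For the questionnaires: "Data on the patients' perceptions and experience of their appliances will be analysed with descriptive statistics to produce graphs and tables". The multilevel model, its fallbacks and the Bonferroni correction all stand in the paragraph on the primary outcome.

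For the face, section 3.2.2 and Table 2 name volumetric change as the outcome. The stereophotogrammetry paragraph of section 6.1 opens by giving soft-tissue volume change as the purpose of the camera. The measurement step it then describes is landmarking of images that are "superimposed to measure the difference in linear distance in millimetres".

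For cost, section 3.2.2 identifies direct costs with the "number of visits for Twinblock phase of treatment and number of breakages/loss with the fixed and removable Twinblock appliances".

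**The concern.** A question of the form *is A more, better or safer than B* needs an estimate of the difference and a statement of how precisely it is known. Section 8.2 provides neither for objectives 2 to 5. This is not a detail left open for a statistical analysis plan. The protocol states a descriptive analysis, and a later plan consistent with it would carry that forward.

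These outcomes are not peripheral. The title says the trial investigates the burden of care, and visits, breakages and patient experience, which are the burden, are all secondary. Two columns of means from small arms invite the reader to pick the larger one.

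The volume point is separate and concerns objective 3 only. A distance between landmarks is not a volume. Someone following section 6.1 to the letter would end with millimetres, and the objective and its outcome would have no matching result.

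**Working it through.** **1. The stated sample size, for context.** Section 8.1 gives a difference of 81 days, SD 101 days, alpha 0.05, power 80% and an independent t-test. Two-sidedness is not stated and is assumed here.

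- d = 81/101 = 0.80.
- The t-test calculation at d = 0.80 gives 25.5, rounded up to 26 per arm (power 0.807 at 26). This agrees with the protocol.
- With 40% dropout, 26/(1 − 0.40) = 43.3, rounded up to 44 per arm and 88 in total. This agrees too.

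There is no arithmetic error. This is the only sample size stated, and no secondary objective has one.

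**2. What a between-arm interval would look like.** For a continuous outcome with equal SDs and n per arm, the 95% half-width in SD units is t(0.975; 2n − 2) × √(2/n).

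| n per arm | t | √(2/n) | Half-width |
|---|---|---|---|
| 26 (completers required) | 2.009 (50 df) | 0.277 | 0.557 SD |
| 44 (all recruited) | 1.988 (86 df) | 0.213 | 0.424 SD |

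An observed difference smaller than the half-width has an interval that includes zero. With 26 per arm, that covers differences up to a little over half an SD.

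**3. What could be detected.** At 80% power and two-sided 0.05, the detectable difference is 0.79 SD with 26 per arm and 0.60 SD with 44. For an assumed true difference of 0.5 SD, power is 42% and 64%. Four tests at 0.05, one per objective and assumed independent, would have a familywise error of 1 − 0.95⁴ = 18.5%. Estimation labelled exploratory therefore suits these outcomes better than a set of significance tests.

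**4. Objective, measurement and analysis side by side.**

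| Objective | Measurement described | Analysis in 8.2 |
|---|---|---|
| 2, skeletal versus dentoalveolar | Cephalometric angles and distances; tooth movement from scans | Descriptive |
| 3, facial volume | Landmark distance in mm; volume named as purpose, with no calculation step | Descriptive |
| 4, experience | Questionnaires at T0, T1, T4 | Graphs and tables |
| 5, cost effectiveness and safety | Visits, breakages/loss, adverse events | Descriptive |

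The last column has no between-arm estimate in any row. The middle column fails to match the first in the row for objective 3. In the row for objective 5, visits and breakages are resource counts rather than costs.

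**The case against.** The strongest reply is that descriptive handling is a legitimate choice. The trial is powered on one endpoint, section 8.2 speaks of exploring the secondary measures, and declining to test several unpowered outcomes avoids multiplicity. That stands as a defence against formal testing. It does not defend leaving out the estimate and its interval, and it does not reconcile a descriptive analysis with objectives worded as comparative questions.

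A reader might infer that the trial cannot answer its secondary objectives. The documents do not support that. Arms are randomised, and section 8.2 promises by-arm summaries. With the group sizes, these let anyone compute an unadjusted difference in means and its interval for a continuous outcome. The uncertainty is left unreported; it is not out of reach.

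A reader might also infer that facial volume is not measured at all. That too goes too far. The 3D images are taken at T0, T4 and T5, and section 6.1 gives volume quantification as their purpose. What is missing is the step from image to volume.

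Finally, one might fault the protocol for giving no unit costs and no rule linking cost to effect. Those details commonly sit in a later analysis or economic plan, so their absence is not a finding. What remains is a label: cost-effectiveness is a strong name for two counts.

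**Conclusion.** The point holds in a limited form. The analysis as written yields no between-arm estimate or uncertainty for four comparative objectives, and objective 3 lacks a measurement step that produces a volume. Both follow from the protocol's own text and need no outside assumption.

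The size, ±0.56 SD at 26 per arm and ±0.42 SD at 44, applies to differences in means of continuous outcomes. It assumes equal SDs and equal arms, with no allowance for centre or baseline. It does not carry over to visits, breakages or adverse events. The detectable differences show that only large effects would be found reliably, which is a reason to show the intervals.

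The primary comparison is not touched. The correction is worth making before results are seen, because choosing afterwards which descriptive differences to interpret is open to selection.

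**What to change.** **Section 8.2.** For each secondary outcome, report the between-arm effect with a 95% confidence interval, labelled exploratory and accounting for centre as in the primary model:

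- a difference in means for continuous outcomes;
- a rate ratio for visits and for breakages/loss;
- a risk difference for adverse events.

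Adjust for the baseline value only where one exists: the cephalometric measures, and 3D measures for which a T0 value is defined. Visits, breakages and adverse events have no baseline. Nor does appliance experience, since the T0 questionnaire asks about the malocclusion and experience is asked only at T1 and T4.

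**Section 6.1, stereophotogrammetry.** Add a volume-change calculation from the superimposed T0, T4 and T5 images. Otherwise reword objective 3 and its outcome to linear soft-tissue change.

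**Objective 5 and the cost outcome.** Call it resource use (visits, breakages/loss) unless costs are attached.

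If the team prefers to stay descriptive, the minimum is to reword objectives 2 to 5 so that they no longer ask a comparative question.

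**Cost.** Protocol wording and some analysis time on data and images already planned, with no extra patients or visits. The intervals will be wide, and some claims will be weaker than the present objectives suggest.
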